# Appendix B

|                                                                                                 |              |             |                     |                     |                |                     |                     |               |                 |                 |              |                   |                   |             |
|-------------------------------------------------------------------------------------------------|--------------|-------------|---------------------|---------------------|----------------|---------------------|---------------------|---------------|-----------------|-----------------|--------------|-------------------|-------------------|-------------|
| Previous cardiac procedure (CABG or PCTA or Stent) + History of CABG or PCTA (for PS) v3; n (%) | 22 (4.5%)    | 14 (2.9%)   | 0.08                | 14 (1.0%)           | 13 (0.9%)      | 0.01                | 91 (5.4%)           | 96 (5.7%)     | -0.01           | 127 (3.6%)      | 123 (3.4%)   | 0.01              |                   |             |
| Diabetes with complication; n (%)                                                               | 35 (7.1%)    | 32 (6.5%)   | #DIV/0!             | 53 (3.8%)           | 50 (3.6%)      | #DIV/0!             | 156 (9.2%)          | 167 (9.8%)    | #DIV/0!         | 53 (3.8%)       | 50 (3.6%)    | 0.01              |                   |             |
| Delirium + Psychosis (for PS); n (%)                                                            | 23 (4.7%)    | 26 (5.3%)   | -0.03               | 30 (2.2%)           | 33 (2.4%)      | -0.01               | 263 (15.5%)         | 262 (15.4%)   | 0.00            | 316 (8.9%)      | 321 (9.0%)   | 0.00              |                   |             |
| Any use of Meglitinides (for PS); n (%)                                                         | 0 (0.0%)     | ** (0.2%)   | -0.06               | ** (0.1%)           | ** (0.1%)      | 0.00                | 0 (0.0%)            | 0 (0.0%)      | #DIV/0!         | #VALUE!         | #VALUE!      | #VALUE!           |                   |             |
| Any use of AGIs (for PS); n (%)                                                                 | 0 (0.0%)     | 0 (0.0%)    | #DIV/0!             | ** (0.1%)           | 0 (0.0%)       | 0.04                | 0 (0.0%)            | 0 (0.0%)      | #DIV/0!         | 0 (0.0%)        | 0 (0.0%)     | #VALUE!           |                   |             |
| CKD stage 3-6 + dialysis (for PS); n (%)                                                        | 16 (3.3%)    | 17 (3.5%)   | -0.01               | 34 (2.5%)           | 25 (1.8%)      | 0.05                | 80 (4.7%)           | 94 (5.5%)     | -0.04           | 130 (3.6%)      | 136 (3.8%)   | -0.01             |                   |             |
| Use of thiazide; n (%)                                                                          | 22 (4.5%)    | 23 (4.7%)   | -0.01               | 79 (5.7%)           | 88 (6.4%)      | -0.03               | 79 (4.6%)           | 82 (4.8%)     | -0.01           | 180 (5.0%)      | 193 (5.4%)   | -0.02             |                   |             |
| Use of beta blockers; n (%)                                                                     | 75 (15.3%)   | 66 (13.5%)  | 0.05                | 231 (16.7%)         | 218 (15.8%)    | 0.02                | 331 (19.5%)         | 328 (19.3%)   | 0.01            | 637 (17.8%)     | 612 (17.1%)  | 0.02              |                   |             |
| Use of calcium channel blockers; n (%)                                                          | 55 (11.2%)   | 56 (11.4%)  | -0.01               | 170 (12.3%)         | 169 (12.2%)    | 0.00                | 194 (11.4%)         | 179 (10.5%)   | 0.03            | 419 (11.7%)     | 404 (11.3%)  | 0.01              |                   |             |
| All antidiabetic medications except Insul                                                       | 57 (11.6%)   | 62 (12.7%)  | -0.03               | 149 (10.8%)         | 158 (11.4%)    | -0.02               | 207 (12.2%)         | 219 (12.9%)   | -0.02           | 413 (11.6%)     | 439 (12.3%)  | -0.02             |                   |             |
| DM Medications -Insulin Copy; n (%)                                                             | 23 (4.7%)    | 27 (5.5%)   | -0.04               | 59 (4.3%)           | 49 (3.5%)      | 0.04                | 80 (4.7%)           | 91 (5.4%)     | -0.03           | 162 (4.5%)      | 167 (4.7%)   | -0.01             |                   |             |
| Use of Low Intensity Statins; n (%)                                                             | 61 (12.4%)   | 63 (12.9%)  | -0.02               | 136 (9.8%)          | 132 (9.6%)     | 0.01                | 283 (16.7%)         | 277 (16.3%)   | 0.01            | 480 (13.4%)     | 472 (13.2%)  | 0.01              |                   |             |
| Use of High Intensity Statins; n (%)                                                            | 51 (10.4%)   | 51 (10.4%)  | 0.00                | 127 (9.2%)          | 132 (9.6%)     | -0.01               | 195 (11.5%)         | 204 (12.0%)   | -0.02           | 373 (10.4%)     | 387 (10.8%)  | -0.01             |                   |             |
| Malignant hypertension; n (%)                                                                   | ** (0.2%)    | ** (0.2%)   | 0.00                | 76 (5.5%)           | 85 (6.2%)      | -0.03               | 82 (4.8%)           | 73 (4.3%)     | 0.02            | #VALUE!         | #VALUE!      | #VALUE!           |                   |             |
| Cardiovascular stress test; n (%)                                                               | ** (1.0%)    | ** (0.4%)   | 0.07                | ** (0.6%)           | ** (0.7%)      | -0.01               | 21 (1.2%)           | 26 (1.5%)     | -0.03           | #VALUE!         | #VALUE!      | #VALUE!           |                   |             |
| Echocardiogram; n (%)                                                                           | 298 (60.8%)  | 349 (71.2%) | -0.22               | 910 (65.9%)         | 960 (69.5%)    | -0.08               | 1,040 (61.2%)       | 1,058 (62.3%) | -0.02           | 2248 (63.0%)    | 2367 (66.3%) | -0.07             |                   |             |
| Number of BNP tests                                                                             | ...mean (sd) |             | 0.17 (0.51)         | 0.22 (0.59)         | -0.09          | 0.15 (0.47)         | 0.17 (0.49)         | -0.04         | 0.17 (0.51)     | 0.22 (0.53)     | -0.10        | 0.16 (0.49)       | 0.20 (0.52)       | 0.00        |
| Number of Cardiac biomarkers tests (tropnin, CK-MBs, Myoglobin, CPK)                            | ...mean (sd) |             | 0.46 (1.22)         | 0.73 (1.68)         | -0.18          | 0.44 (1.13)         | 0.54 (1.46)         | -0.08         | 0.39 (0.80)     | 0.46 (0.96)     | -0.08        | 0.42 (1.00)       | 0.53 (1.28)       | 0.00        |
| Number of Ambulatory Blood pressure monitoring tests                                            | ...mean (sd) |             | 0.00 (0.00)         | 0.00 (0.06)         | 0.00           | 0.00 (0.04)         | 0.00 (0.03)         | 0.00          | 0.00 (0.00)     | 0.00 (0.00)     | #DIV/0!      | 0.00 (0.02)       | 0.00 (0.03)       | 0.00        |
| N of days on antihypertensive medications during baseline                                       | ...mean (sd) |             | 41.64 (66.76)       | 40.37 (67.11)       | 0.02           | 45.23 (70.39)       | 45.62 (70.62)       | -0.01         | 41.49 (66.16)   | 43.81 (67.50)   | -0.03        | 42.96 (67.91)     | 44.04 (68.67)     | 0.00        |
| N of days in database anytime prior                                                             | ...mean (sd) |             | 1,631.36 (1,356.14) | 1,568.20 (1,247.77) | 0.05           | 2,203.52 (1,550.45) | 2,092.63 (1,508.64) | 0.07          | 720.02 (502.47) | 681.78 (392.54) | 0.08         | 1418.98 (1141.20) | 1349.21 (1080.43) | 0.00        |
| Mean Copay for per prescription cost (charges in U.S. \$) (180-1 day prior)                     | ...mean (sd) |             | 22.31 (49.02)       | 22.88 (47.07)       | -0.01          | 11.22 (16.38)       | 10.92 (16.98)       | 0.02          | 111.13 (120.49) | 117.56 (187.51) | -0.04        | 60.29 (85.70)     | 63.31 (130.97)    | 0.00        |
| ...Missing; n (%)                                                                               | 57 (11.6%)   |             | 59 (12.0%)          | -0.01               | 156 (11.3%)    | 155 (11.2%)         | 0.00                | 182 (10.7%)   | 179 (10.5%)     | 0.01            | 395 (11.1%)  | 393 (11.0%)       | 0.00              |             |
| Colonoscopy; n (%)                                                                              | 17 (3.5%)    |             | 20 (4.1%)           | -0.03               | 55 (4.0%)      | 50 (3.6%)           | 0.02                | 47 (2.8%)     | 47 (2.8%)       | 0.00            | 119 (3.3%)   | 117 (3.3%)        | 0.00              |             |
| Fecal occult blood (FOB) test; n (%)                                                            | 14 (2.9%)    |             | 14 (2.9%)           | 0.00                | 47 (3.4%)      | 45 (3.3%)           | 0.01                | 33 (1.9%)     | 43 (2.5%)       | -0.04           | 94 (2.6%)    | 102 (2.9%)        | -0.02             |             |
| Flu vaccine; n (%)                                                                              | 62 (12.7%)   |             | 57 (11.6%)          | 0.03                | 142 (10.3%)    | 144 (10.4%)         | 0.00                | 440 (25.9%)   | 432 (25.4%)     | 0.01            | 644 (18.0%)  | 633 (17.7%)       | 0.01              |             |
| Mammogram; n (%)                                                                                | 43 (8.8%)    |             | 49 (10.0%)          | -0.04               | 138 (10.0%)    | 152 (11.0%)         | -0.03               | 152 (8.9%)    | 138 (8.1%)      | 0.03            | 333 (9.3%)   | 339 (9.5%)        | -0.01             |             |
| Pap smear; n (%)                                                                                | 26 (5.3%)    |             | 23 (4.7%)           | 0.03                | 98 (7.1%)      | 106 (7.7%)          | -0.02               | 48 (2.8%)     | 54 (3.2%)       | -0.02           | 172 (4.8%)   | 183 (5.1%)        | -0.01             |             |
| Pneumonia vaccine; n (%)                                                                        | 94 (19.2%)   |             | 85 (17.3%)          | 0.05                | 179 (13.0%)    | 178 (12.9%)         | 0.00                | 506 (29.8%)   | 501 (29.5%)     | 0.01            | 779 (21.8%)  | 764 (21.4%)       | 0.01              |             |
| PSA test or Prostate exam for DRE; n (%)                                                        | 42 (8.6%)    |             | 39 (8.0%)           | 0.02                | 132 (9.6%)     | 132 (9.6%)          | 0.00                | 134 (7.9%)    | 122 (7.2%)      | 0.03            | 308 (8.6%)   | 293 (8.2%)        | 0.01              |             |
| Bone mineral density; n (%)                                                                     | ** (1.8%)    |             | 15 (3.1%)           | -0.08               | 20 (1.4%)      | 21 (1.5%)           | -0.01               | 39 (2.3%)     | 42 (2.5%)       | -0.01           | #VALUE!      | 78 (2.2%)         | #VALUE!           |             |
| Use of CNS stimulants; n (%)                                                                    | ** (1.8%)    |             | ** (1.8%)           | -0.02               | ** (0.5%)      | 26 (1.5%)           | -0.13               | ** (0.6%)     | ** (0.6%)       | 0.00            | #VALUE!      | #VALUE!           | #VALUE!           |             |
| Use of estrogens, progestins, androgens; r                                                      | 48 (9.8%)    |             | 42 (8.6%)           | 0.04                | 175 (12.7%)    | 176 (12.7%)         | 0.00                | 62 (3.6%)     | 65 (3.8%)       | -0.01           | 285 (8.0%)   | 283 (7.9%)        | 0.00              |             |
| Use of Angiogenesis inhibitors; n (%)                                                           | 0 (0.0%)     |             | ** (0.2%)           | -0.06               | ** (0.1%)      | ** (0.1%)           | 0.00                | ** (0.1%)     | ** (0.2%)       | -0.03           | #VALUE!      | #VALUE!           | #VALUE!           |             |
| Use of Oral Immunosuppressants; n (%)                                                           | ** (0.2%)    |             | ** (0.2%)           | 0.00                | ** (0.4%)      | ** (0.2%)           | 0.04                | ** (0.2%)     | ** (0.2%)       | 0.00            | #VALUE!      | #VALUE!           | #VALUE!           |             |
| Use of fondaparinux or Bivalirudin; n (%)                                                       | 0 (0.0%)     |             | 0 (0.0%)            | #DIV/0!             | ** (0.1%)      | ** (0.1%)           | 0.00                | ** (0.2%)     | ** (0.1%)       | 0.03            | #VALUE!      | #VALUE!           | #VALUE!           |             |
| Use of other direct thrombin inhibitors (I                                                      | 0 (0.0%)     |             | 0 (0.0%)            | #DIV/0!             | 0 (0.0%)       | #DIV/0!             | 0 (0.0%)            | 0 (0.0%)      | #DIV/0!         | 0 (0.0%)        | 0 (0.0%)     | #DIV/0!           | 0 (0.0%)          | #DIV/0!     |
| Use of Ticagrelor ON CED; n (%)                                                                 | 0 (0.0%)     |             | 0 (0.0%)            | #DIV/0!             | ** (0.1%)      | 0 (0.0%)            | 0.04                | 0 (0.0%)      | ** (0.1%)       | -0.04           | #VALUE!      | #VALUE!           | #VALUE!           |             |
| Use of Ticagrelor; n (%)                                                                        | 0 (0.0%)     |             | 0 (0.0%)            | #DIV/0!             | ** (0.1%)      | ** (0.1%)           | 0.00                | 0 (0.0%)      | ** (0.2%)       | -0.06           | #VALUE!      | #VALUE!           | #VALUE!           |             |
| Number of D-dimer tests                                                                         | ...mean (sd) |             | 0.19 (0.44)         | 0.19 (0.45)         | 0.00           | 0.17 (0.44)         | 0.18 (0.45)         | -0.02         | 0.19 (0.45)     | 0.18 (0.43)     | 0.02         | 0.18 (0.44)       | 0.18 (0.44)       | 0.00        |
| Number of CRP, high-sensitivity CRP tests                                                       | ...mean (sd) |             | 0.13 (0.58)         | 0.14 (0.77)         | -0.01          | 0.10 (0.45)         | 0.09 (0.49)         | 0.02          | 0.13 (0.59)     | 0.13 (0.57)     | 0.00         | 0.12 (0.54)       | 0.12 (0.57)       | 0.00        |
| Number of PT or aPTT tests                                                                      | ...mean (sd) |             | 1.03 (2.16)         | 1.03 (2.17)         | 0.00           | 0.85 (2.00)         | 0.81 (1.96)         | 0.02          | 0.53 (1.12)     | 0.52 (1.10)     | 0.01         | 0.72 (1.67)       | 0.70 (1.65)       | 0.00        |
| Number of Bleeding time tests                                                                   | ...mean (sd) |             | 0.00 (0.00)         | 0.00 (0.00)         | #DIV/0!        | 0.00 (0.00)         | 0.00 (0.00)         | #DIV/0!       | 0.00 (0.00)     | #DIV/0!         | 0.00 (0.00)  | 0.00 (0.00)       | #DIV/0!           | 0.00 (0.00) |
| HAS-BLED Score (ICD-9 and ICD-10), 180 days                                                     | ...mean (sd) |             | 2.06 (0.69)         | 2.07 (0.63)         | -0.02          | 1.90 (0.70)         | 1.90 (0.68)         | 0.00          | 2.38 (0.81)     | 2.39 (0.78)     | -0.01        | 2.15 (0.75)       | 2.16 (0.72)       | 0.00        |
| N of Generic name drugs                                                                         | ...mean (sd) |             | 14.39 (14.69)       | 14.42 (16.73)       | 0.00           | 11.78 (10.46)       | 12.02 (13.21)       | -0.02         | 19.11 (18.82)   | 19.05 (19.03)   | 0.00         | 15.63 (15.51)     | 15.70 (16.68)     | 0.00        |
| N of Brand name drugs                                                                           | ...mean (sd) |             | 2.59 (4.40)         | 2.63 (2.88)         | -0.01          | 2.47 (3.76)         | 2.53 (2.57)         | -0.02         | 3.47 (5.81)     | 3.51 (3.78)     | -0.01        | 2.96 (4.92)       | 3.01 (3.24)       | 0.00        |
| Use of clopidogrel; n (%)                                                                       | ** (0.6%)    |             | ** (0.8%)           | -0.02               | ** (0.5%)      | ** (0.5%)           | 0.00                | 68 (4.0%)     | 62 (3.6%)       | 0.02            | #VALUE!      | #VALUE!           | #VALUE!           |             |
| Systemic embolism; n (%)                                                                        | ** (1.8%)    |             | 12 (2.4%)           | -0.04               | 26 (1.9%)      | 28 (2.0%)           | -0.01               | 29 (1.7%)     | 29 (1.7%)       | 0.00            | #VALUE!      | 69 (1.9%)         | #VALUE!           |             |
| DVT; n (%)                                                                                      | 257 (52.4%)  |             | 248 (50.6%)         | 0.04                | 757 (54.8%)    | 739 (53.5%)         | 0.03                | 824 (48.5%)   | 849 (50.0%)     | -0.03           | 1838 (51.5%) | 1836 (51.4%)      | 0.00              |             |
| Post-thrombotic syndrome; n (%)                                                                 | 0 (0.0%)     |             | 0 (0.0%)            | #DIV/0!             | ** (0.1%)      | ** (0.1%)           | #DIV/0!             | ** (0.2%)     | ** (0.1%)       | #DIV/0!         | ** (0.1%)    | ** (0.1%)         | 0.00              |             |
| PE; n (%)                                                                                       | 490 (100.0%) |             | 490 (100.0%)        | #DIV/0!             | 1,381 (100.0%) | 1,381 (100.0%)      | #DIV/0!             | 1,692 (99.6%) | 1,695 (99.8%)   | -0.04           | 3563 (99.8%) | 3566 (99.9%)      | -0.03             |             |
| Coagulation defects; n (%)                                                                      | ** (1.6%)    |             | ** (2.2%)           | #DIV/0!             | 35 (2.5%)      | 40 (2.9%)           | #DIV/0!             | 28 (1.6%)     | 32 (1.9%)       | 35 (2.5%)       | 40 (2.9%)    | -0.02             |                   |             |
| Diabetes: 1 inpatient or 2 outpatient clai                                                      | 86 (17.6%)   |             | 90 (18.4%)          | -0.02               | 212 (15.4%)    | 210 (15.2%)         | 0.01                | 371 (21.8%)   | 407 (24.0%)     | -0.05           | 669 (18.7%)  | 707 (19.8%)       | -0.03             |             |

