## 9. Balance Assessment

**Action report links:**

Optum: <https://bwh-dope.aetion.com/projects/details/1484/results/64541/result/0>

Marketscan: <https://bwh-dope.aetion.com/projects/details/1481/results/64542/result/0>

Medicare: <https://bwh-dope.aetion.com/projects/details/1483/results/64543/result/0>

Date conducted: 1/19/2021

After review of initial feasibility and power analyses, complete creation of the remaining covariates from Section 6.2. Again, using the dummy outcome of a 90-day gap in database enrollment, complete a 1:1 PS-matched analysis. The PS should include the complete list of covariates.

- Provide plot of PS distributions stratified by treatment group.

Note- Please refer to **Appendix B**.

- Report covariate balance after matching.

Note- For Table 1, please refer to **Appendix B**.

- Report reasons for censoring by treatment group.

|  | Overall | Referent | Exposure |
|--|---------|----------|----------|
|--|---------|----------|----------|

|                                                                                                                               |                |                |                |
|-------------------------------------------------------------------------------------------------------------------------------|----------------|----------------|----------------|
| Dummy outcome                                                                                                                 | 67 (0.94%)     | 25 (0.70%)     | 42 (1.18%)     |
| Death                                                                                                                         | 103 (1.44%)    | 49 (1.37%)     | 54 (1.51%)     |
| Start of an additional exposure                                                                                               | 232 (3.25%)    | 175 (4.90%)    | 57 (1.60%)     |
| End of index exposure                                                                                                         | 4,701 (65.84%) | 2,202 (61.68%) | 2,499 (70.00%) |
| Specified date reached                                                                                                        | 857 (12.00%)   | 424 (11.88%)   | 433 (12.13%)   |
| End of patient enrollment                                                                                                     | 425 (5.95%)    | 198 (5.55%)    | 227 (6.36%)    |

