## 10. Final Power Assessment

Date conducted: 12/16/20

- Re-calculate power in the appropriate excel table, using the revised number of matched patients from the PS-match in Section 9. All other parameters in the table should be the same as in Section 8.
  - Pooled

Effectiveness research with Real World Data to support FDA's regulatory decision making

| Non-inferiority Analysis |             |
|---------------------------------|-------------|
| Number of patients matched      | 7,140       |
| Reference                       | 3,570       |
| Exposed                         | 3,570       |
| Risk per 1,000 patients         | 13.74       |
| HR from RCT                     | 0.84        |
| Alpha (2-sided)                 | 0.05        |
| Non-inferiority margin          | 1.8         |
|                                 |             |
| Number of events expected       | 98.1036     |
| Power                           | 0.965194245 |

- Optum

| Non-inferiority Analysis |             |
|---------------------------------|-------------|
| Number of patients matched      | 980         |
| Reference                       | 490         |
| Exposed                         | 490         |
| Risk per 1,000 patients         | 12.93       |
| HR from RCT                     | 0.84        |
| Alpha (2-sided)                 | 0.05        |
| Non-inferiority margin          | 1.8         |
|                                 |             |
| Number of events expected       | 12.6714     |
| Power                           | 0.273097221 |

○ Marketscan

| Non-inferiority Analysis |             |
|---------------------------------|-------------|
| Number of patients matched      | 2,762       |
| Reference                       | 1,381       |
| Exposed                         | 1,381       |
| Risk per 1,000 patients         | 13.13       |
| Assumed HR from RCT             | 0.84        |
| Alpha (2-sided)                 | 0.05        |
| Non-inferiority margin          | 1.8         |
|                                 |             |
| Number of events expected       | 36.26506    |
| Power                           | 0.631133873 |

o Medicare

| Non-inferiority Analysis   |             |
|----------------------------|-------------|
| Number of patients matched | 3,398       |
| Reference                  | 1,699       |
| Exposed                    | 1,699       |
| Risk per 1,000 patients    | 14.66       |

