# Appendix B

The c-statistics for the propensity score model, pre-matching was 0.938. The postmatching c-statistic was 0.684.

[figure not shown]
[figure not shown]
[figure not shown]

The c-statistics for the propensity score model, pre-matching was 0.848. The postmatching c-statistic was 0.572.

The c-statistics for the propensity score model, pre-matching was 0.874. The postmatching c-statistic was 0.566.

AFTER PS MATCHING

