| Age categories without zero category                                              |                      |                     |           |                      |                     |           |                      |                     |           |                      |                     |           |
| ...18 - 54; n (%)                                                                 | 201 (41.0%)          | 184 (37.6%)         | 0.07      | 726 (52.6%)          | 748 (54.2%)         | -0.03     | 449 (26.4%)          | 453 (26.7%)         | -0.01     | 1,376 (38.5%)        | 1,385 (38.8%)       | -0.01     |
| ...55 - 64; n (%)                                                                 | 167 (34.1%)          | 170 (34.7%)         | -0.01     | 568 (41.1%)          | 547 (39.6%)         | 0.03      | 494 (29.1%)          | 475 (28.0%)         | 0.02      | 1,229 (34.4%)        | 1,192 (33.4%)       | 0.02      |
| ...65 - 74; n (%)                                                                 | 54 (11.0%)           | 87 (17.8%)          | -0.19     | 53 (3.8%)            | 48 (3.5%)           | 0.02      | 383 (22.5%)          | 427 (25.1%)         | -0.06     | 490 (13.7%)          | 562 (15.7%)         | -0.06     |
| ...>75; n (%)                                                                     | 68 (13.9%)           | 49 (10.0%)          | 0.12      | 34 (2.5%)            | 38 (2.8%)           | -0.02     | 373 (22.0%)          | 344 (20.2%)         | 0.04      | 475 (13.3%)          | 431 (12.1%)         | 0.04      |
| Gender without zero category- United                                              |                      |                     |           |                      |                     |           |                      |                     |           |                      |                     |           |
| ...Males; n (%)                                                                   | 240 (49.0%)          | 229 (46.7%)         | 0.05      | 727 (52.6%)          | 709 (51.3%)         | 0.03      | 786 (46.3%)          | 781 (46.0%)         | 0.01      | 1,753 (49.1%)        | 1,719 (48.2%)       | 0.02      |

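### Matching in Optum leaves echocardiogram, cardiac biomarker tests and age category more imbalanced than before, and the pooled column prints two related differences as 0.00

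*Combined protocol and SAP*

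**What the plan says.** Section 9 (Balance Assessment) calls for a 1:1 PS-matched analysis on a dummy outcome and states "The PS should include the complete list of covariates". Section 6.2 places the full covariate list in Table 1 of Appendix B. That table includes the rows "Echocardiogram; n", "Number of Cardiac biomarkers tests (tropnin, CK-MBs, Myoglobin, CPK", number of BNP tests, and "Age categories without zero category", both unmatched and matched, so all four are already collected.

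Appendix B gives three pairs of c-statistics. The highest after matching is reported as "The postmatching c-statistic was 0.684"; the other two are 0.572 and 0.566. The text available for this review does not label them by database.

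Section 10 stops the work until investigators, FDA and advisory board members have reviewed balance. No section gives an SMD limit for acceptable balance, lists the terms of the fitted PS, or says what happens to a covariate that stays imbalanced. Section 13 (Comparative Analyses) is still blank.

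**The concern.** A well-fitted PS that contains a covariate should bring the groups closer on it, or at least not drive them apart. In Optum several listed covariates moved the wrong way. Echocardiogram, troponin-type and BNP testing measure how intensively a patient was worked up. Nearly all matched patients have PE (99.8% and 99.9% pooled), and the primary outcome rests on hospital admission for VTE, so work-up intensity and age could plausibly be related to the outcome. If they are, the remaining difference may bias the HR.

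The second problem is one of reporting. A reader at the balance stop who goes to the pooled column sees 0.00 for two of these rows and would conclude that nothing is left.

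**Working it through.** **Inputs.** Counts, means and SDs come from the unmatched and PS-matched tables of Appendix B. Matched sizes come from Section 10: "Number of patients matched | 980" in Optum, "Number of patients matched | 2,762" in MarketScan, "Number of patients matched | 3,398" in Medicare, that is 490, 1,381 and 1,699 per arm.

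**Formulas** (warfarin minus apixaban, so a negative value means more on apixaban).
- Binary rows: SMD = (p0 - p1) / sqrt{[p0(1-p0) + p1(1-p1)] / 2}.
- Count rows: SMD = (m0 - m1) / sqrt[(s0² + s1²) / 2].

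**Step 1: reproduce the printed matched values.**
- Optum echocardiogram: 298/490 = 0.608 and 349/490 = 0.712. SMD = -0.104 / 0.471 = -0.221 (printed -0.22).
- Optum biomarker tests: (0.46 - 0.73) / sqrt[(1.22² + 1.68²)/2] = -0.27 / 1.468 = -0.184 (printed -0.18).
- Optum age 65-74: 54/490 = 0.110 and 87/490 = 0.178. SMD = -0.067 / 0.349 = -0.19 (printed -0.19).
- The nine matched SMDs for echocardiogram, biomarker and BNP tests all agree with the printed values to two decimals.

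**Step 2: compare before and after matching** (printed SMDs, recomputed where the rounding matters).

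| Row | Optum | MarketScan | Medicare |
|---|---|---|---|
| Echocardiogram | -0.16 to -0.22 | -0.13 to -0.08 | -0.05 to -0.02 |
| Cardiac biomarker tests | -0.11 to -0.18 | -0.07 to -0.08 | -0.09 to -0.08 |
| BNP tests | -0.10 to -0.09 | -0.09 to -0.04 | -0.05 to -0.10 |
| Age 65-74 | -0.05 to -0.19 | 0.03 to 0.02 | -0.10 to -0.06 |
| Age >75 | 0.05 to 0.12 | 0.03 to -0.02 | 0.02 to 0.04 |

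Other rows show what the matching did achieve. Optum heparin use went from 1.39 to -0.03, and Optum brand-name drugs from -0.35 to -0.01. PT/aPTT tests went from 0.20 / 0.17 / 0.39 to 0.00 / 0.02 / 0.01 (Optum / MarketScan / Medicare).

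**Step 3: compare with chance.** With 490 per arm, the SE of an SMD under simple randomisation is about sqrt(2/490) = 0.064. The Optum echocardiogram gap is 0.221/0.064, about 3.5 SE. This is descriptive only: the row was picked from a long table after inspection.

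**Step 4: recompute the pooled matched values.**
- Echocardiogram: 63.0% vs 66.3%, SMD -0.070 (printed -0.07).
- BNP tests: (0.16 - 0.20) / sqrt[(0.49² + 0.52²)/2] = -0.04 / 0.505 = -0.079; between -0.10 and -0.06 allowing for rounding of the inputs (printed 0.00).
- Biomarker tests: (0.42 - 0.53) / sqrt[(1.00² + 1.28²)/2] = -0.11 / 1.149 = -0.096; between -0.105 and -0.087 (printed 0.00).

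**Step 5: illustrate possible bias.** The documents give no association between these covariates and the outcome, so a risk ratio RR is assumed for echocardiogram. Bias factor = [1 + p1(RR-1)] / [1 + p0(RR-1)].

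| Assumed RR | Optum | Pooled |
|---|---|---|
| 1.5 | 1.040 | 1.013 |
| 2 | 1.065 | 1.020 |
| 3 | 1.094 | 1.030 |

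With 98.1 expected events, SE(log HR) is about sqrt(4/98.1) = 0.20. A pooled factor of 1.03 is ln(1.03)/0.20, about 0.15 SE.

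**The case against.** The strongest reply concerns scope. Only Optum clearly exceeds 0.10, which is itself an outside convention. Optum supplies 980 of 7,140 matched patients and about 12.7 of 98.1 expected events. The pooled gaps are 0.07 to 0.10 in absolute size, and the illustration above gives a small pooled bias. All of this stands.

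A reader might infer that apixaban patients had more severe PE in all three databases and that the HR is therefore biased. The documents do not support that:
- No section describes these rows as severity markers or ties the tests to the index event.
- Neighbouring rows do not follow: D-dimer tests are 0.00 / -0.02 / 0.02, any electrocardiogram is -0.08 / 0.01 / 0.01, and hospital days are slightly higher on warfarin in all three databases.
- That nine of nine signs agree is weaker than it looks. These are three related variables on the same patients, all skewed this way before matching.
- If more work-up did mean higher risk, the bias would raise apixaban's HR, which works against a false non-inferiority finding.

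A reader might also infer that the variables were omitted from the PS. That is possible, but the fitted terms are not listed; poor fit would look the same. On age, mean age in Optum is balanced (-0.02), so the problem lies in the distribution across categories.

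Finally, the printed 0.00 is not peculiar to these rows. Pooled matched INR tests (0.62 vs 0.50) and days in database also print 0.00, which suggests a table-formula fault. And Section 10 already imposes a balance review. That review does not replace a correction, because the pooled column is wrong for these rows and there is no rule for residual imbalance.

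**Conclusion.** The point holds for Optum. Echocardiogram (-0.22), cardiac biomarker tests (-0.18) and age category (-0.19 and +0.12) remain imbalanced and are worse than before matching, which is hard to square with a well-fitted PS holding the complete covariate list. In MarketScan and Medicare the three test rows agree in direction but not in material size. Separately, the pooled SMDs for BNP and biomarker tests are misprinted as 0.00 and should read about -0.08 and -0.10.

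The imbalance may bias the HR. The size cannot be computed from the documents and, under the assumed risk ratios above, would be small in the pooled estimate. Whether these rows reflect PE severity, care setting or neither is open. The change is worth making because the covariates are in hand and the comparative analysis has not been recorded as run.

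**What to change.** Before Section 13 is carried out:
1. List the terms of each database's fitted PS. Confirm that echocardiogram, cardiac biomarker tests, BNP tests and age category are in each, and respecify the Optum model. Alternatively, adjust for these four in the outcome model, stratified by database, at least as a sensitivity analysis.
2. State a balance rule and apply it within each database as well as pooled, for example absolute SMD of 0.10 or less (an outside convention), and say what is done with covariates that miss it. Such a rule would also flag INR tests (0.17 in Optum, 0.12 in MarketScan), so their handling should be stated too.
3. Recompute the pooled SMDs for all count rows in Appendix B and put the corrected table before the Section 10 reviewers.

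The cost is a PS re-run or a few model terms, and possibly some lost Optum pairs. Because Section 9 works on a dummy outcome, the PS can be respecified without seeing comparative results.
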